5.6 APPROPRIATENESS OF MEASUREMENTS

All measurements performed during this trial are standard measurements and will be performed in order to monitor subjects' safety and to determine pharmacokinetic parameters in an appropriate way. The scheduled measurements will allow monitoring of changes in vital

Proprietary confidential information © 2018 Boehringer Ingelheim International GmbH or one or more of its affiliated companies

signs, standard laboratory values, and ECG parameters that might occur as a result of administration of trial medication. The safety assessments are standard, are accepted for evaluation of safety and tolerability of an orally and intravenously administered drug, and are widely used in clinical trials. The pharmacokinetic parameters and measurements outlined in Section [5.4](#) are generally used assessments of drug exposure.

6. INVESTIGATIONAL PLAN

6.1 VISIT SCHEDULE

Exact times of measurements outside the permitted time windows will be documented. The acceptable time windows for screening and the end-of-trial examination are provided in the [Flow Chart](#).

Study measurements and assessments scheduled to occur 'before' trial medication administration on Day 1 are to be performed and completed within a 3 h-period prior to the trial drug administration.

The acceptable deviation from the scheduled time for vital signs, ECG, and laboratory tests will be \pm 30 min on Day 1 and \pm 180 min on the following days of Visit 2.

If several activities, including 12-lead ECG and meal intake, are scheduled at the same time point in the [Flow Chart](#), ECG should be the first and meal intake the last activity.

Furthermore, if several measurements including venepuncture are scheduled for the same time, venepuncture should be the last of the measurements due to its inconvenience to the subject and possible influence on physiological parameters.

For planned blood sampling times refer to the [Flow Chart](#). While these nominal times should be adhered to as closely as possible, the actual sampling times will be recorded and used for the determination of pharmacokinetic parameters.

If a subject misses an appointment, it will be rescheduled if possible. The relevance of measurements outside the permitted time windows will be assessed no later than at the Report Planning Meeting.

6.2 DETAILS OF TRIAL PROCEDURES AT SELECTED VISITS

6.2.1 Screening period

Screening visit is defined as Visit 1.

After having been informed about the trial, all subjects will provide written informed consent in accordance with GCP and local legislation prior to enrolment in the study.

For information regarding laboratory tests (including drug and virus screening), ECG, vital signs, and physical examination, refer to Sections [5.2.1](#) to [5.2.5](#).

6.2.2 Treatment period

Each subject is expected to participate in one treatment period (Visit 2).

On Day -1 of Visit 2, study participants will be admitted to the trial site and kept under close medical surveillance for at least 24 h following administration of treatment T. The subjects will then be allowed to leave the trial site after formal assessment and confirmation of their fitness. On all other study days, subjects will be treated in an ambulatory fashion.

Proprietary confidential information © 2018 Boehringer Ingelheim International GmbH or one or more of its affiliated companies

For details on time points and procedures for collection of plasma samples for PK analysis, refer to [Flow Chart](#) and Section [5.3.2](#).

The safety measurements performed during the treatment period are specified in Section [5.3](#) of this protocol and in the [Flow Chart](#). For details on times of all other trial procedures, refer to the [Flow Chart](#). AEs and concomitant therapy will be assessed continuously from screening until the end of trial examination.

6.2.3 Follow-up period and trial completion

For AE assessment, laboratory tests, recording of ECG and vital signs, and physical examination during the follow-up period, see Sections [5.2.1](#) to [5.2.5](#).

Subjects who discontinue treatment before the end of the planned treatment period should undergo the EoTrial Visit.

All abnormal values (including laboratory parameters) that are assessed as clinically relevant by the investigator will be monitored using the appropriate tests until a return to a medically acceptable level is achieved. (S)AEs persisting after a subject's EoTrial Visit must be followed until they have resolved, have been sufficiently characterised, or no further information can be obtained.

7. STATISTICAL METHODS AND DETERMINATION OF SAMPLE SIZE

7.1 STATISTICAL DESIGN – MODEL

The main objective of this trial is to investigate the absolute bioavailability of 50 mg BI 730357 administered as tablet (test treatment, T) compared with 2 µg of labelled [C-14]BI 730357 BS administered as intravenous microtracer (mixed with 98 µg unlabelled BI 730357), (reference treatment, R) on the basis of the primary pharmacokinetic endpoints, as listed in Sections [2.1.2](#). The trial is designed to allow intra-subject comparisons and will be evaluated statistically by use of an appropriate linear model.

The assessment of safety and tolerability is a further objective of this trial, and will be evaluated by descriptive statistics for the parameters specified in Section [2.2.2.2](#).

7.2 NULL AND ALTERNATIVE HYPOTHESES

The absolute bioavailability of 50 mg orally administered BI 730357 compared with 2 µg of labelled [C-14]BI 730357 administered as intravenous microtracer (mixed with 98 µg unlabelled BI 730357) will be estimated by the ratio of the geometric means (test/reference) for the dose-normalized primary PK endpoints. Additionally, their 2-sided 90% confidence intervals (CIs) will be provided. This method corresponds to the two one-sided t-test procedure, each at the 5% significance level. Since the main focus is on estimation and not testing, a formal hypothesis test and associated acceptance range is not specified.

Confidence intervals have to be interpreted in the perspective of the exploratory character of the study, i.e. confidence intervals are considered as interval estimates for effects.

7.3 PLANNED ANALYSES

Analysis sets

Statistical analyses will be based on the following analysis sets:

- Treated set (TS): The treated set includes all subjects who were randomized and treated with at least one dose of study drug. The treated set will be used for safety analyses.
- Pharmacokinetic parameter analysis set (PKS): This set includes all subjects in the treated set (TS) who provide at least one PK endpoint that was defined as primary and was not excluded due to a protocol deviation relevant to the evaluation of PK or due to PK non-evaluability (as specified in the following subsection ‘Pharmacokinetics’). Thus, a subject will be included in the PKS, even if he contributes only one PK parameter value for the study period to the statistical assessment. Descriptive and model based analyses of PK parameters will be based on the PKS.

Proprietary confidential information © 2018 Boehringer Ingelheim International GmbH or one or more of its affiliated companies

Adherence to the protocol will be assessed by the trial team. Important protocol deviation (IPD) categories will be suggested in IQRM plan, IPDs will be identified no later than in the Report Planning Meeting, and the IPD categories will be updated as needed.

Pharmacokinetics

The pharmacokinetic parameters listed in Section [2.1](#) for drug BI 730357 will be calculated according to the relevant SOP of the Sponsor ([001-MCS-36-472](#)).

Plasma concentration data and parameters of a subject will be included in the statistical pharmacokinetic (PK) analyses if they are not flagged for exclusion due to a protocol deviation relevant to the evaluation of PK (to be decided no later than in the Report Planning Meeting) or due to PK non-evaluability (as revealed during data analysis, based on the criteria specified below). Exclusion of a subject's data will be documented in the CTR.

Relevant protocol deviations may be

- Incorrect trial medication taken, i.e. the subject received at least one dose of trial medication the subject was not assigned to
- Incorrect dose of trial medication taken
- Use of restricted medications

Plasma concentrations and/or parameters of a subject will be considered as non-evaluable, if for example

- The subject experienced emesis that occurred at or before two times median t_{max} of the respective treatment (median t_{max} is to be determined excluding the subjects experiencing emesis),
- A predose concentration is $>5\%$ C_{max} value of that subject
- Missing samples/concentration data at important phases of PK disposition curve

Plasma concentration data and parameters of a subject which is flagged for exclusion will be reported with its individual values but will not be included in the statistical analyses.

Descriptive and inferential statistics of PK parameters will be based on the PKS.

Only concentration values within the validated concentration range and actual sampling times will be used for the calculation of pharmacokinetic parameters. Concentrations used in the pharmacokinetic calculations will be in the same format provided in the bioanalytical report, (that is, to the same number of decimal places provided in the bioanalytical report).

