Visit	Day	Planned time (relative to first drug administration) [h:min]	Approximate clock time of actual day [h:min]	Event and comment	Safety laboratory	PK plasma BI 730357	PK plasma [C-14]BI 730357 BS	12-lead ECG	Vital signs (BP, PR)	Local tolerability assessment	Questioning for AEs and concomitant therapy ⁷
1	-21 to -2			Screening (SCR) ¹	x						
2	-1	-18:00	14:00	Admission to trial site	x ⁵			x	x		
		-14:00	18:00	Dinner							
		-10:30	21:30	Light supper (voluntary) ⁸							
	1	-2:00	06:00			x ^{2,3}	x ³	x ³	x ³		
		0:00	08:00	Drug administration (50 mg BI 730357 as tablet, oral)							
		1:00	09:00			x					
		1:15	09:15	Start of IV infusion containing BI 730357 BS (C-14)							
		1:20	09:20				x				
		1:25	09:25				x				
		1:30	09:30	Stop of IV infusion		x	x				
		1:45	09:45			x				x	
		2:00	10:00	240 mL fluid intake		x	x	x			
		2:30	10:30			x	x				
		3:30	11:30			x	x				
		4:00	12:00	240 mL fluid intake				x	x		
		5:00	13:00	Lunch ⁴		x	x				
		7:00	15:00			x	x				
		11:00	19:00	Dinner							
		12:00	20:00			x	x				
	2	24:00	08:00	Breakfast (voluntary) ⁴ , discharge from trial site	x	x	x	x	x	x	
	4	72:00	08:00	Ambulatory visit ⁹		x	x				
	6	120:00	08:00	Ambulatory visit ⁹	x	x	x				
	8	168:00	08:00	Ambulatory visit ⁹		x	x				
3	9 to 15			End-of-trial (EoTrial) examination ⁶	x			x	x		x

1. Subject must be informed and written informed consent obtained prior to starting any screening procedures. Screening procedures include physical examination, check of vital signs, ECG, safety laboratory (including drug screening), demographics (including determination of body height and weight, smoking status and alcohol history), relevant medical history, concomitant therapy and review of inclusion/exclusion criteria.
2. Including pharmacogenomics sample
3. The time is approximate; the procedure is to be performed and completed within 3 h prior to drug administration.
4. If several actions are indicated at the same time point, the intake of meals will be the last action.
5. Safety lab including urine drug and alcohol screening.
6. At the end-of-trial visit, the EoTrial examination includes physical examination, vital signs, ECG, safety laboratory, recording of AEs and concomitant therapies.
7. AEs and concomitant therapies will be recorded throughout the trial; during in-house days subjects will be specifically asked for twice daily.

Proprietary confidential information © 2018 Boehringer Ingelheim International GmbH or one or more of its affiliated companies

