3.3.5 Replacement of subjects

In case a subject vomits within 12 h after oral trial drug administration suggesting an incomplete absorption of the tablet or a subject drops out for other reasons, an additional subject may be entered and dosed to ensure that 6 subjects will complete the study as per protocol. In total, no more than 2 subjects will be replaced.

Proprietary confidential information © 2018 Boehringer Ingelheim International GmbH or one or more of its affiliated companies

In case some subjects do not complete the trial, the Trial Clinical Monitor together with the Trial Pharmacokineticist and the Trial Statistician are to decide, if and how many subjects will be replaced. Replacement of subjects and dosing of additional subjects as described above should always be done in mutual agreement with the principal investigator. A replacement subject will be assigned a unique trial subject number.

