4.1.5 Blinding and procedures for unblinding

This Phase I trial will be handled in an open fashion throughout (that is, during the conduct, including data cleaning and preparation of the analysis). This is considered acceptable because the potential for bias seems to be low and does not outweigh practical considerations.

Emergency envelopes will not be provided because the dose of trial medication is known to investigators and subjects.

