6.2 IMPORTANT PROTOCOL DEVIATIONS

Data discrepancies and deviations from the CTP will be identified for all subjects enrolled in this trial.

Consistency check listings (for identification of deviations from time windows) and a list of protocol deviations (e.g. deviations in drug administration, in blood sampling times, etc.) will be provided to be discussed at the medical quality review meeting, the blinded report planning and database lock meeting (RPM/DBLM). At this meeting, it will be decided whether a discrepant data value can be used in analyses or whether it must be corrected in the clinical database. Each protocol deviation must be assessed to determine whether it is an important protocol deviation (iPD). For definition of iPDs, and for the process of identification of these, refer to the Boehringer Ingelheim (BI) SOP "Integrated Quality and Risk Management Process" ([2](#)).

If any iPDs are identified, they are to be summarised into categories and will be captured in the RPM/DBLM minutes via an accompanying excel spreadsheet. Categories which are considered to be iPDs in this trial are defined in the integrated quality and risk management plan (IQRMP). If the data show other iPDs, the definition in the IQRMP will be supplemented accordingly by the time of the RPM/DBLM.

iPDs will be summarised and listed.

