6.3 SUBJECT SETS ANALYSED

All entered subjects who received study medication will be included in the safety analysis and in the PK analysis depending on the availability of measurement values, and on their adherence to the CTP.

The following subject sets will be defined for statistical analysis:

- Treated set (TS):
This subject set includes all subjects who received at least one dose of study drug. This is the full analysis set population in the sense of ICH-E9 ([1](#)). It will be used for analysis of safety, demographic data and baseline characteristics.
- Pharmacokinetic parameter set (PKS):
This subject set includes all subjects in the TS who provide at least one primary PK

parameter that was not excluded because of protocol deviations relevant to the statistical evaluation of PK endpoints as defined in Section 7.3 of the CTP.

The discussion of all exceptional cases and problems and the decisions on the allocation of subjects to analysis sets will be made at latest at the RPM/DBLM.

Table 6.3: 1 Subject sets analysed

Class of endpoint	Subject set	
	TS	PKS
Disposition	X	
Exposure	X	
iPDs	X	
Demographic/baseline endpoints	X	
Safety parameters	X	
Primary PK endpoint		X
Further PK endpoints		X

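### Does the plan leave open whether the oral AUC of a subject who vomits after twice the median tmax, but within 12 h, enters the bioavailability estimate?

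*Protocol*

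**What the plan says.** Protocol 3.3.5 allows an additional subject to be entered "In case a subject vomits within 12 h after oral trial drug administration suggesting an incomplete absorption of the tablet", or after dropout for other reasons. At most 2 subjects are replaced, so 6 become at most 8.

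For the analysis, Protocol 7.3 includes a subject's concentrations and parameters unless they are flagged. There are two grounds for a flag: a relevant protocol deviation, decided by the Report Planning Meeting, or exclusion "due to PK non-evaluability (as revealed during data analysis, based on the criteria specified below"). The criteria are introduced by "Plasma concentrations and/or parameters of a subject will be considered as non-evaluable, if for example". The emesis item reads "The subject experienced emesis that occurred at or before two times median" tmax of the treatment concerned, with the median taken without the subjects who vomited. Exclusions are documented in the trial report, and excluded values are still reported individually.

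The SAP has no emesis rule of its own. Section 6.3 refers to Protocol 7.3 and adds that "the decisions on the allocation of subjects to analysis sets will be made at latest at the RPM/DBLM". Section 7.4 works with an inclusion/exclusion flag on each PK parameter. Section 6.2 speaks of "the blinded report planning and database lock meeting (RPM/DBLM"), whereas Protocol 4.1.5 says the trial is "handled in an open fashion throughout (that is, during the conduct, including data cleaning and preparation of the analysis").

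**The concern.** The protocol uses two emesis limits, 12 h and twice the observed median tmax, and comments only on what each is for. A subject who vomits between them may be replaced on a suspicion of incomplete absorption, yet he meets no listed criterion for exclusion. Because that list is illustrative, someone could still argue for removing him.

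The cut-off also depends on the observed median tmax, so the oral profiles are known when it is applied. One document has non-evaluability emerge during the analysis. The other fixes set allocation at a meeting that it calls blinded.

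F with its 90% interval is the trial's only primary estimate, from 6 to 8 subjects. If the in-or-out choice were free and the subject had lost much of his dose, the estimate would depend on a decision taken with the AUCs in view. Keeping one subject with a 50% loss among 7 would lower F by 9%. Two such subjects among 8 would lower it by 16%.

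**Working it through.** **1. The plan's own figure.** 6 planned + 2 replacements = 8 at most, as stated. No precision calculation is given, so there is nothing further to reproduce.

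**2. The window.** Its length is 12 h − 2 × median tmax. The Flow Chart has oral samples at 1:00, 1:30, 1:45, 2:00, 2:30, 3:30, 5:00, 7:00 and 12:00 h. Protocol 3.1 expects tmax at 1.25 h.

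| Median tmax (h) | Cut-off (h) | Window (h) |
|---|---|---|
| 1.0 | 2.0 | 10 |
| 1.25 | 2.5 | 9.5 |
| 2.5 | 5.0 | 7 |
| 3.5 | 7.0 | 5 |
| 5.0 | 10.0 | 2 |

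The window closes at a median tmax of 6 h or more.

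**3. What the text gives inside the window.** Under 3.3.5 an extra subject may be dosed. Under 7.3 the data are included unless flagged, and the emesis criterion is not met, so the AUC stays in. Section 3.3.5 removes nobody from the analysis. Excluding later emesis under the illustrative wording would leave the stated cut-off without a function.

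**4. Effect on F if he stays in.** With k affected subjects among n, each losing a fraction L of the oral AUC, F is multiplied by (1 − L)^(k/n). L is not in the documents.

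| L (assumed) | 1 of 7 | 2 of 8 |
|---|---|---|
| 0% | 1.000 | 1.000 |
| 10% | 0.985 | 0.974 |
| 25% | 0.960 | 0.931 |
| 50% | 0.906 | 0.841 |

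**5. How large L can plausibly be.** Vomiting can lose only drug not yet absorbed. Assume one compartment with first-order absorption (ka) and elimination (ke), and let r = ka/ke. Then tmax = ln(r)/(ka − ke), so ka × tmax = r ln(r)/(r − 1). The fraction unabsorbed at 2 × tmax is exp(−2r ln(r)/(r − 1)).

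- r = 1 (limit): exp(−2) = 0.135. One case in 7: 0.865^(1/7) = 0.979.
- r = 5: exp(−4.02) = 0.018. Factor 0.997.
- r = 10: exp(−5.12) = 0.006. Factor 0.999.

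These figures take everything unabsorbed at the first instant of the window as lost. The loss falls with time after that.

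A larger figure arises if ka and tmax are chosen separately. With ka = 0.5 per h and a cut-off of 2.0 h, exp(−1.0) = 0.37 is unabsorbed. But a tmax of 1.0 h with ka = 0.5 per h requires ke of about 1.76 per h (0.5 × exp(−0.5) = 0.303 = 1.76 × exp(−1.76)). That is an elimination half-life of 0.693/1.76 = 0.4 h, which sits poorly with sampling to 168 h and a 7-day residual effect period. A 50% loss exceeds even the 37%.

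**6. Against the precision of the trial.** Assume an SD of 0.2 for log(T/R). The 90% confidence factor is exp(t × s/√n).

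- Out, n = 6: exp(2.015 × 0.2/√6) = 1.18.
- In, n = 7, L = 13.5%: s² = 0.04 + ln(0.865)²/7 = 0.0430, so s = 0.207 and the factor is exp(1.943 × 0.207/√7) = 1.16.

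Keeping him moves F by about 2%, well inside the interval, and does not widen it.

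**7. Timing and blinding.** SAP 6.3 concerns allocation to analysis sets. Under Protocol 7.3 one primary parameter is enough for membership of the PK set, so a subject with a valid i.v. AUC belongs to it whatever happens to his oral AUC. Dropping the oral AUC is a parameter flag under SAP 7.4, which carries no deadline. A finding made during the analysis is therefore compatible with the set-allocation deadline. Calling the meeting blinded does conflict with Protocol 4.1.5, but with one arm there is no code to conceal.

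**The case for a change.** The strongest case is that inclusion is a default and not a stated rule. The list of criteria is open, Protocol 3.3.5 itself links vomiting up to 12 h with incomplete absorption, and the choice could be made with the AUCs known. One sentence would close it at almost no cost. The SAP's definition of the PK set also names only protocol deviations, where the protocol names non-evaluability as well.

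Some of this stands. The illustrative wording does leave residual discretion, and the two SAP phrases are loose. The bound in step 5 is also model-based. The protocol calls the compound BCS class II and mentions solubility limitations, and absorption slower than elimination, or multi-compartment kinetics, could leave more than 13.5% unabsorbed. At a 25% loss, one case in 7 moves F by 4%; at 37% it moves F by 6% (0.63^(1/7) = 0.94). Both remain smaller than the interval half-width in step 6.

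The discretion is also visible. The listed cut-off uses the recorded emesis time and a median tmax computed without the subjects who vomited, and does not use the subject's own AUC. Any exclusion must be reported with the individual values, so a reader can recompute F the other way. The cited sponsor PK procedure may hold a further rule; it was not available.

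**Conclusion.** No change is needed. Read as written, Protocol 7.3 keeps the oral AUC of a subject who vomits after twice the median tmax, and the 12 h limit serves a different decision. An analyst following the text would reach a sound estimate.

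The likely effect of one such case among 7 is a reduction in F of about 2% or less. This assumes one-compartment first-order kinetics with absorption at least as fast as elimination, and total loss of whatever is unabsorbed at the cut-off. It arises only if someone vomits in the window. The documents give no emesis rate; an assumed 1% to 5% per subject gives 1 − 0.99^6 = 6% to 1 − 0.95^6 = 26% for at least one case among 6 at any time, of which only part would fall in the window. The intervals are declared exploratory and have no acceptance range, so no decision turns on a shift of this size.

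The blinded label in SAP 6.2 and the shorter PK-set wording in SAP 6.3 are clerical. They can be tidied if the document is reopened, but the result does not depend on them. Nothing here takes a view on either emesis limit.
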